##### **a) Serious Adverse Event Reporting**

Study patients are instructed to contact the clinic with any serious adverse event meeting the above criteria. Each SAE is recorded on the study form and the PI is informed as soon as possible after they occur and preferably within 24 hours of the notification of the clinic staff. This notification should occur even if data are incomplete. Additional data and follow-up information are documented and sent subsequently as an update to the original report. The PI immediately forwards SAE reports to the COMIRB and any other required institutional monitoring committee.

### C. Participant Discontinuation Criteria

If a participant experiences any of the following, the participant will be withdrawn from the study.

1. Inability to complete study procedures
2. Abnormal screening labs (LFT's >125 IU, HbA1C>6.4%, Hg <11 mg/dL)
3. Participant becomes pregnant during study

### D. Protocol Stopping Criteria

If one or more participants experience any of the SAE's listed above, the PI will consult with the study staff prior to continuing study visits with participants. The PI and RSA will consult about the significance of the SAE's and make a recommendation about participant continuation in the study.

## VII. Data Analysis Plan:

### Overall Project Statistical Plan:

Sample size analysis: Sample size is based on the power to detect a change in IHTG with treatment with EAA as compared to placebo (primary endpoint). Assuming a 2-sided  $\alpha=0.05$ , 20 participants provides 86% power to detect a change of 2.8% in IHTG, assuming a 3.9% standard deviation of change, which corresponds to a correlation of 0.8 between repeated measures. For Aim secondary measures, a 2 sample size of 20 gives 99% power to detect a change of 14.4 mg/dL in 2 hour OSTT glucose and 81% power to detect a change of 1.8 in HOMA-IR, assuming a standard deviation of 14.4 mg/dL and 2.7, respectively. Estimates of effect size and variability were conservatively estimated from the PI's extensive pilot data.

Analysis plan: No interim analyses are planned. Prior to the start of any formal analyses, unusual values that need to be queried, patterns of missing values, and whether their distributions are non-Gaussian will be identified. Demographic and clinical characteristics will be summarized with descriptive statistics. Analyses will follow the "intent-to-treat" principle so that study hypotheses are tested under realistic conditions in which not all participants adhere to the intervention. For the primary outcome, we will compare IHTG with and without EAA treatment using a paired t-test or a Wilcoxon signed rank test. Similar analyses will be used for secondary outcomes (2 hour OSTT glucose, HOMA-IR, metabolomics markers, proportion of direct/indirect glucose, EAA concentrations). Linear models will be used to identify the variables that are associated with change in IHTG, such 2 hour OSTT glucose, HOMA-IR, metabolomics markers, etc.

All measures will be adjusted for OSA status (yes/no) and/or severity of AHI.

Secondary outcomes include a Pearson correlation test of potentially related variables followed by targeted multiple regression to assess the relationship between hepatic fat and adipose IR, PEP, TCA, TG synthesis pathways.

Likely contributors to endpoints: Variables known to affect IHTG and IR will be measured: lipid/glucose markers (lipid panel, HbA1c); inflammatory markers (C-reactive protein, AST, ALT, GGT); glucose-related hormones (glucagon, GLP-1 and leptin), sex-steroids (DHEA-S, free and total testosterone, sex hormone binding globulin, progesterone, estradiol); body composition (BMI, waist:hip ratio, lean and fat mass by DEXA); Variations in diet, activity, menstrual phase and circadian rhythms affect metabolism and will be assessed: dietary intake (7 day food diary), habitual activity (3 day questionnaire and accelerometer for 7 days prior to study) and sleep timing and quality (sleep questionnaires and sleep and light watch). OSTT studies will be performed in the morning fasting, in the follicular phase of the menstrual cycle where possible, preceded by 3 days of no strenuous physical activity and a typical diet for the participant.

Non-Isotope OSTT calculations: The Matsuda model of IR will be used but adapted for the 6.5 hour OSTT, and B-cell function [insulinogenic index ( $\Delta I30/\Delta G30$ ) and ( $\Delta C30/\Delta G30$ ) and disposition index ( $1/IFasting \times \Delta I30/\Delta G30$ ) and ( $1/CFasting \times \Delta C30/\Delta G30$ ) will be calculated. Differences between groups will be evaluated with and without controlling for activity and sleep status.

Fitting glucose and glycerol concentrations curves: Using computed data points, glycerol and glucose concentrations will be fitted with an appropriate model. In control participants, concentration typically shows 3 phases in OSTT. Cubic polynomial, piecewise-linear, spline, and dynamic models have been used for fitting Ra in previous work. We will assume a cubic polynomial model; we will validate estimates obtained with the cubic polynomial model by computing comparable estimates using at least one other model form. In previous work comparing different models (piecewise-linear, cubic polynomial, dynamic), results have been relatively unaffected by choice of model. If we find that this is not the case for our data, then we would certainly consider the advantages of adopting a more complex approach, such as the state-space, for describing concentration changes.

Metabolomics data: Differences in targeted metabolic concentrations will be compared between groups, after appropriate cleaning of the data, as performed by the processing site. Changes in metabolites over time will be compared between groups, to determine the times that demonstrate the largest differences. Results will also be compared to isotopomer results, to see if a metabolomics endpoint can yield similar information to the isotopomer analysis.

Gut Microbiota: The microbiota profile is entirely exploratory, and will be related to status of hepatic steatosis and 2 hour glucose status of impaired glucose tolerance or not.

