### Overall enrollment procedure plan per group

#### VISIT 1 (SCREEN VISIT)

Pediatric CTRC Outpatient unit: Participants will begin with a medical screening and physical exam for inclusion/exclusion criteria evaluation. During this visit, patients will review and complete consent documents, have demographics and medical history confirmed, assess allergies and further evaluation of inclusion/exclusion criteria, have blood samples drawn, and have anthropometrics completed. HbA1c, ALT, AST, CBC panel and testosterone panel will be drawn at the beginning of the visit after consent in all participants. PCOS labs may be performed for confirmation of PCOS status, if not performed previously. Whole blood for DNA samples for future genetic analysis associated with hepatic steatosis will also be drawn and stored at this time. Participants will also have a Fibroscan (liver ultrasound) to check for HS (CAP score of >225).

After eligibility assessment, participants who qualify for the study will be randomized to placebo or EAA by the pharmacy. Both study staff and participant will be blinded. The participant will be scheduled for Visits 2 and 3 after being on placebo or EAA supplements for 4 weeks.

Screening lab test	Purpose for test
HbA1C	Rule out type 2 diabetes, if > 6.4% participant to be excluded
ALT, AST	Ensure no severe liver disease, if >125 IU/L participant to be excluded normal participant is excluded
Hemoglobin & Hematocrit (part of CBC)	If participant is Anemic, they will be excluded
Testosterone	Test for hyperandrogenism – required to meet NIH criteria for PCOS
Optional PCOS labs	
PCOS status must be confirmed prior to enrollment. Referring physicians often do not perform the entire recommend work-up for oligomenorrhea (per 2013 Endocrine Society Clinical Guidelines for PCOS). The values are typically expected in PCOS publications	
TSH, total T4	Ensure no hypo or hyperthyroidism causing amenorrhea
LH, FSH	Rule out primary ovarian failure
17-hydroxyprogesterone	Rule out late onset congenital adrenal hyperplasia
DHEAS	Rule out adrenal tumor
Prolactin	Rule out prolactin secreting brain tumor

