## LIFESTYLE PRESCRIPTION

1) At the time of screening, all participants will receive standard lifestyle recommendations including the reduction of liquid carbohydrate and portion control. We will not perform extensive counseling at this time as major changes in diet could affect the results. However, variability in the consumption of sugar sweetened beverage may affect results, and thus we will discourage these in all participants. Further this is the first step of standard lifestyle counseling for this population.

2) The final visit will conclude with education regarding the importance of physical activity, diet and lifestyle modification to mediate the risks associated with sedentary lifestyle and an exercise prescription designed to increase physical activity. The information at this visit will build on the previous education, and be personalized to include the basal metabolic rate calculations and specific dietary recommendations based on the food frequency survey. The exercise information and prescription are the standard of care used in our Children's Hospital Colorado Pediatric Metabolic Syndrome Clinic, designed by the Children's Hospital Colorado Pediatric Exercise Physiologist. Families will be provided with standard information about follow up care with their primary care provider and contact information for Children's Hospital Colorado Diabetes and Child Health Clinics if needed regarding any abnormal study findings. In addition, the participant/family will be provided with copies of their study lab results, DEXA scan and physical activity monitoring. A results letter will be provided to the family within 6 months of completion of the study about clinically relevant results obtained during the study. Participants will be encouraged to contact study staff with questions regarding the results letter.

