### **Overall Project Limitations:**

We expect to complete 20 participants in 2.5 years. As with any clinical trial, recruitment and retention can be challenging. We have successfully recruited over 120 obese girls with untreated PCOS, and thus our recruitment goals are in line with previous work. We have never needed to recruit in the community or other endocrinology practices, but can if needed. Within our department we have been successful with 3 month, 21 month and 3 year interventional protocols and we have designed the study with techniques found to be successful in similarly obese adolescent populations. Adherence to treatment is also a challenge, and we will use texting and emails as preferred contacts in youth to send supplement reminders. Major changes to diet and exercise could alter results, and we will request participants not to initiate major lifestyle changes during the study. An alternative would be to recommend lifestyle changes for all girls, although from our clinical experience these are poorly followed.

**Aim 1:** We anticipate that after EAA, absolute IHTG will decrease by 3% compared to placebo, secondary to decreased DNL. Based the mean of  $11 \pm 3.5\%$  IHTG in PCOS girls with HS, this is less than the relative 50% decrease we found in most of older adult participants. Further, 9 days of low fructose dietary modification reduced IHTG by 50% via decreased DNL in obese youth with HS, demonstrating that IHTG can be rapidly changed with dietary modification and relates to decreased DNL. However, this patient population does have a very poor diet, and it is possible that those with excessive soda intake will not benefit as anticipated if EAA cannot overcome the excess glucose. An alternative would be to provide the diet for participants for 3 days prior to studies. We will be using a FibroScan ultrasound based method to determine the presence of HS at screening. MRI is the most sensitive and repeatable measure for IHTG. Ideally we would also perform an MRI for IHTG at screening to determine eligibility, however the cost and time of this for the 50% of girls to be excluded is excessive and the processing time for the results is not conducive for a screening test. Whereas our lab has not used deuterated water to measure DNL, this method has been used successfully in other youth populations by our collaborator [name], and we thus are confident that we will be able to perform this analysis.

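### The crossover's primary test has no period term; a period-adjusted mixed model would guard against a period shift at small cost

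*Combined protocol and SAP*

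**What the plan says.** The Overall Study Design section describes a 12-week blinded crossover: 4 weeks each of EAA and placebo, about 4 weeks of washout, and metabolic studies after each treatment. Under Visit 1, "participants who qualify for the study will be randomized to placebo or EAA by the pharmacy"; neither the allocation ratio nor any blocking is stated. The Study Calendar places the liver MRI only at Visits 2 and 4, so there is no scan before treatment.

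Under Overall Project Statistical Plan, the primary analysis is: "we will compare IHTG with and without EAA treatment using a paired t-test or a Wilcoxon signed rank test". No rule is given for choosing between the two tests. No period or sequence term appears anywhere in section VII. The adjustments it names are OSA status or AHI severity for all measures, and activity and sleep for the OSTT calculations. Missing-value patterns are to be identified, but no handling method is given. Intent-to-treat is declared and explained by reference to girls who do not adhere.

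The sample size statement is that "20 participants provides 86% power to detect a change of 2.8% in IHTG". The same paragraph takes the SD of the within-girl difference as 3.9 points and equates this with a within-girl correlation of 0.8.

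**The concern.** In a two-period crossover each girl's EAA-minus-placebo difference contains the treatment effect plus or minus any change between periods. The sign depends on which treatment she takes first. A paired test cannot separate the two. With equal sequences the change adds spread to the differences; with unequal sequences part of it is also reported as treatment effect.

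The protocol offers one plausible source of such a change. At screening, "all participants will receive standard lifestyle recommendations including the reduction of liquid carbohydrate and portion control". That advice is given once, before period 1, and may fade or build over the following weeks. The Overall Project Limitations section says that 9 days of low-fructose diet cut IHTG by 50%, so the outcome can respond to diet. Without a pre-treatment MRI, drift cannot be checked against a baseline.

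At stake are the power and the conditional accuracy of the only primary comparison in a 20-girl trial.

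**Working it through.** **Inputs.** From the statistical plan: N = 20, two-sided alpha 0.05, difference 2.8 percentage points, SD of the within-girl difference 3.9. From the Recruitment paragraph: about 5% dropout. Assumptions, because the documents give no figure: a period shift of 0 to 2.8 points, and the sequence splits shown.

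**The plan's own figure.** Noncentrality = 2.8 / (3.9/√20) = 3.21 on 19 df, which gives 86.1% power. The stated 86% reproduces, so the sample size arithmetic for this test is not at issue.

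**Model.** Let τ be the treatment effect and π the change from period 1 to period 2. The EAA-minus-placebo difference is τ + π + error for girls taking EAA second (n1) and τ − π + error for girls taking it first (n2). The error SD is 3.9.

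- Paired mean: expectation τ + π(n1 − n2)/N.
- Period-adjusted estimate: the average of the two sequence means, with expectation τ for any π. Its standard error is (3.9/2)√(1/n1 + 1/n2), on 18 df.

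**Equal sequences (10:10).** There is no bias, but the expected variance of the differences becomes 3.9² + π² × 20/19. The SD rises from 3.9 to √(15.21 + 2.06) = 4.16 at π = 1.4, and to √(15.21 + 8.25) = 4.84 at π = 2.8. Simulation with 100,000 trials per setting gives:

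| Shift | Paired t power | Period-adjusted power | Paired t type I error |
|---|---|---|---|
| 0 | 86% | 86% | 5.0% |
| 1.4 | 83% | 86% | 3.8% |
| 2.8 | 73% | 86% | 1.7% |

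The paired test is therefore conservative here.

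**Unequal sequences (13:7), conditional on that split.** Bias = π × 6/20, which is 0.42 points at π = 1.4 and 0.84 at π = 2.8, or 15% and 30% of the 2.8 effect.

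- If the shift works against EAA, paired power is 70% or 40%, against 82.5% adjusted.
- If it works in favour of EAA, an effect of 2.8 is estimated as about 3.2 or 3.6.
- Conditional type I error of the paired test is 7.3% at π = 2.8.
- Under simple 1:1 randomisation (an assumption), a split of 13:7 or worse has probability 26%.

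**Averaged over simple 1:1 randomisation.** Mean bias of the paired test is zero and its type I error is 5% at every shift tried.

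| Shift | Paired t power | Period-adjusted power |
|---|---|---|
| 0 | 86% | 84% |
| 1.0 | 84% | 84% |
| 1.4 | 82% | 84% |
| 2.8 | 69–70% | 84% |

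**Cost of adjusting when there is no shift.** At 10:10, power goes from 86.1% to 85.9%. At 13:7 the standard error is 1.95 × √(1/13 + 1/7) = 0.914, and power is 82.5%.

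**Girls with one scan.** Five percent of 20 is one girl. With 19 complete pairs the period-adjusted power is 83.8%. Adding her single scan through the mixed model raises it to between 83.9% and 84.3%, for a correlation between 0.8 and 0.38. The lower correlation is what SD 3.9 implies with the between-girl SD of 3.5 in the limitations section: 1 − 3.9²/(2 × 3.5²) = 0.38. The gain is under 1 point.

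**The case against.** The strongest defence is that the paired test is valid on average. If sequence is assigned by simple 1:1 randomisation, the sign of the period effect is itself random, so the estimate is unbiased and type I error is 5%. The 7.3% figure needs both one unlucky split and the largest assumed shift. This stands, and a reader should not infer that the planned test inflates type I error overall. What remains is that, once the split is known to be unequal, the estimate is displaced by a predictable multiple of the shift, and the paired test does nothing about it.

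A reader might also infer that a period effect is likely. The documents do not support that. Both MRIs come after the screening advice. If diet acts within days and the change persists, it is present at both scans and cancels. The protocol limits counselling at screening, says from clinical experience that lifestyle recommendations are poorly followed, and keeps the fuller education for the final visit, after the last MRI. The shifts of 1.4 and 2.8 are illustrations, and for shifts up to about 1 point adjustment gains nothing on average.

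Finally, a reader might infer that intent-to-treat is breached because a paired test cannot use a girl with one scan. The plan explains intent-to-treat in terms of adherence, and non-adherent girls with both scans stay in. Nowhere does it say that one-period girls are dropped; that follows only from the choice of test. The plan aims for 20 completers and allows extra enrolment. With about one such girl expected, this is a small matter and not a demonstrated breach.

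**Conclusion.** The point holds as a cheap improvement that should be made. The primary test of a two-period crossover omits period. If there is a real shift, the cost at 10:10 is about 3 power points for 1.4 and about 13 for 2.8, with a conservative test. At 13:7 it is a conditional bias of 0.42 or 0.84 points. Averaged over simple 1:1 randomisation, the loss relative to adjustment is about 2 points at 1.4 and 14 to 15 at 2.8, and nil up to about 1 point.

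These sizes rest on the plan's SD of 3.9 and effect of 2.8, on normal errors, and on shifts and splits that are assumed. Blocking is unstated, which does not show that it is absent; if sequences are balanced among the analysed girls, only the loss of power applies. The documents do not support a claim of unconditional bias, of overall type I inflation or of a probable period effect.

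**What to change.** Replace the primary analysis with a linear mixed model of end-of-period MRI IHTG:

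- fixed effects for treatment, period and sequence, a random participant effect, and Kenward–Roger degrees of freedom;
- every randomised girl with at least one MRI included;
- EAA minus placebo reported with its 95% confidence interval.

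For complete pairs this equals the two-sample t-test on period differences. Use the same model for the continuous secondary outcomes, and keep a rank test on period differences as a sensitivity analysis.

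The model can also carry the OSA/AHI adjustment that the plan promises for all measures and that a paired t or signed rank test cannot accommodate. The SAP should say which AHI value is used, since the sleep study is scheduled at both overnight visits.

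The change is to SAP wording only. With no period effect, power goes from 86.1% to about 85.9% at 10:10, to about 84% on average under simple randomisation, and to about 82.5% at 13:7.

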### **VISIT 3 (ORAL GLYCEROL TRACER WITH D2O AND ORAL SUGAR TOLERANCE TEST)**

Children's Hospital Colorado or University Hospital CTRC Inpatient unit Only under extenuating circumstances, if no rooms available in either hospital, we may have patients go home after WatchPAT is placed, and drink deuterated water at home, and come back the following morning at 6am: Participants will be asked not to have caffeine or exercise for 3 days prior to this visit. During admission, participant will be provided with a study diet dinner and snack. Patients will be admitted to the Pediatric CTRC for a monitored overnight fast. Participants will be questioned regarding changes in concomitant medications and medical history, height, weight, BP. Participants will also have a Fibroscan (liver ultrasound) on the day of admission or the morning of the OSTT (pending staff availability).

A DEXA scan will be performed to assess body composition. A urine pregnancy test will be done on all female participants prior to the DEXA scan. If a female participant is confirmed to be pregnant, she will be withdrawn from the study and referred to her primary care physician for follow-up.

The following morning, a blood sample for baseline metabolic labs will be drawn the modified OSTT will be completed (**Figure 10**). Additional blood will be drawn and stored for future inflammatory markers as well as for targeted and untargeted metabolomics analysis.

WatchPAT: During the hospital overnight stay, trained study staff will place the WatchPAT sleep monitor. The primary measures will be for oxygen saturation and apnea hypopnea index (AHI). Each participant will wear the watch with a one-time use finger cuff as recommended by the FDA. The watch will be placed by 8 PM, and will be removed the following morning. The watch pat data collection will not be ideal, due to waking the participants to drink the deuterated water. However, the primary endpoint is the apnea hypopnea index, and we can still get a rough estimate of this information, even with less than ideal sleep.

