### Follow-up from Sleep study results:

As discussed above, we anticipate that approximately 30-40% of our participants will have an abnormal apnea hypopnea index (AHI), requiring some type of follow-up. We have worked with Drs. [name], [name] and [name], our primary pediatric sleep pulmonologists to develop a post-study follow-up algorithm. Of note, [name] is currently working with Kaiser to verify the accuracy of the results from the WatchPAT device as compared to inpatient polysomnograms in children younger than 12, and is very familiar with this device, it's output and limitations. Our youth fall into a grey zone in terms of what is an abnormal sleep study, as pediatric criteria are defined for less than 12, and adult for 18 or older. The international accepted clinical criteria are listed below, as well as the American Academy of Sleep Medicine's recommendations of how to handle age 12-17:

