**16. WatchPAT and Questionnaires to assess for Obstructive Sleep Apnea**

*Description:* The WatchPAT is a noninvasive portable system that measures the oxygen saturation and apnea hypopnea index. Three surveys querying signs and symptoms of obstructive sleep apnea.

*Risk:* No risk associated with the questionnaires and the WatchPAT, other than a mild discomfort from having to wear the watch and cuff around finger during sleep. It is possible that we will discover that the participant has obstructive sleep apnea, and will need to be referred for further clinical care.

*Justification:* Obstructive sleep apnea is associated with obesity, and can worsen both fatty liver and insulin resistance. Thus the presence of OSA must be accounted for when measuring either of these outcomes. These surveys selected are currently being utilized by the NIH multiple center study in obese youth at risk for diabetes, and are well validated in youth from multi-ethnic populations. If OSA is suspected during the course of the screen, the participants will be referred for further evaluation and treatment. The WatchPAT is an FDA approved device that can be used specifically for oxygen saturation and apnea hypopnea index and is approved in children as young as 12 years of age, within the age range of our study population.

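### The plan adjusts every outcome for OSA/AHI, which is measured only after treatment in each period and has no place in the named paired test; the model, visit and cut-off are left open.

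*Combined protocol and SAP*

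**What the plan says.** Under Overall Project Statistical Plan (section VII), IHTG with and without EAA is compared by a paired t-test or a Wilcoxon signed rank test, and secondary outcomes are handled in a similar way. Linear models are mentioned for finding variables associated with change in IHTG. A separate one-line paragraph then states: "All measures will be adjusted for OSA status (yes/no) and/or severity of AHI". It names no visit, cut-off or model.

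The Study Calendar marks the WatchPAT sleep study at Visits 3 and 5 only. The Visit 1 description and the note closing the Visit 3 description place both overnight visits after four weeks on product. Screening includes no sleep measure.

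Section III.D, item 16, gives the reason for adjusting. It says that OSA can worsen fatty liver and insulin resistance, and concludes: "Thus the presence of OSA must be accounted for when measuring either of these outcomes". The Visit 3 text concedes that waking girls to drink deuterated water disturbs the recording, but says "we can still get a rough estimate of this information, even with less than ideal sleep". The section on follow-up of sleep results expects an abnormal AHI in 30-40% of participants.

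The sample size paragraph says that "20 participants provides 86% power to detect a change of 2.8% in IHTG", "assuming a 3.9% standard deviation of change".

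**The concern.** The rule covers all measures, so on its face it covers the primary endpoint, yet the test named for that endpoint cannot apply it. Whoever analyses the data must either ignore the sentence or replace the test with a model that the plan does not describe.

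The covariate is also measured after treatment in both periods. Conditioning on a variable that treatment may have changed can take out part of the treatment effect. The and/or wording allows a binary term, a continuous term or both, from either visit, so each outcome can have several adjusted results with no rule for choosing among them. In a trial of 20 completers, the primary estimate should not depend on a choice made after the data are seen.

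**Working it through.** **Inputs from the plan.** 20 completers; two-sided alpha 0.05; IHTG difference 2.8 points; SD of the within-girl difference 3.9; abnormal AHI in 30-40%, that is 6-8 of 20.

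**Assumed, because the documents give no figure.** The share of the EAA effect that runs through AHI: 0%, 10%, 25% or 50%. The correlation between a girl's AHI difference and her IHTG difference: 0.3 or 0.5.

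**1. The plan's own power.** SE = 3.9/√20 = 0.872. Noncentrality = 2.8/0.872 = 3.21. With 19 df the noncentral t gives 86.1%, against 86% stated. The stated power is therefore that of the unadjusted paired t-test.

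**2. OSA status constant across the two periods.** In a within-girl model this term is collinear with the participant effect. In simulated data the EAA estimate with and without it agreed to rounding error. Adjustment does nothing here.

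**3. Paired difference regressed on an uncentred OSA 0/1 term.** The intercept is the effect in OSA-negative girls, with SE = 3.9/√n₀ on 18 df:

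| OSA-negative girls (n₀) | SE | Power for 2.8 points |
|---|---|---|
| 14 (30% with OSA) | 1.04 | 72% |
| 13 (35%) | 1.08 | 69% |
| 12 (40%) | 1.13 | 65% |

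If the term is mean-centred, the intercept is again the average over all 20 girls. Power is then 85.9% (18 df, residual SD kept at 3.9).

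**4. Paired difference regressed on the between-period difference in AHI.** This is equivalent to a participant-effects model that carries each visit's AHI. Let D be the IHTG reduction on EAA relative to placebo and x the AHI difference in SD units:

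D = 2.8 × (1 − share) + b·x + error, with b = correlation × 3.9 and mean of x = share × 2.8 / b.

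The total SD of D stays at 3.9. The adjusted estimate is the intercept at x = 0, with expected value 2.8 × (1 − share). For a 25% share this is 2.8 × 0.75 = 2.1. Power is by simulation and is good to about a percentage point:

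| Share through AHI | Adjusted estimate | Power, correlation 0.3 | Power, correlation 0.5 |
|---|---|---|---|
| 0% | 2.8 | 87% | 92% |
| 10% | 2.5 | 77% | 86% |
| 25% | 2.1 | 52% | 67% |
| 50% | 1.4 | 17% | 29% |

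The unadjusted paired test stays at 2.8 points and about 86% in every row.

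**The case against.** The best defence is that the sentence was never meant for the paired test. It comes after the linear models and before the correlation and multiple regression plans, and may belong to those. The paired test, run as written, is unadjusted and keeps its 86%. That reading is possible, but a rule for all measures does not say so, and the plan should.

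The harm is also conditional, and this stands. Nothing in the documents shows that EAA changes AHI within four weeks. If none of the effect runs through AHI, adjusting for it causes no bias and may gain a little power. The 65-72% figure needs both uncentred coding and the intercept reported as the overall effect, and the plan specifies neither.

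OSA need not be constant either. Visit 3 sleep studies are read within five business days and abnormal results are followed up, so a girl's OSA could change before the second period. Cancellation is then incomplete, but randomised order still protects the unadjusted contrast from systematic bias on this account.

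Under Non-Isotope OSTT calculations, the plan offers results with and without control for sleep status. That helps for those indices but does not reach IHTG.

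A reader might infer from the paediatric and adult AHI bands that OSA yes/no also encodes age. Those bands belong to the clinical follow-up of sleep findings, and the plan never says that they define OSA for analysis. The supportable point is that no cut-off is given.

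**Conclusion.** The concern holds as a fault in specification and in what is estimated. The plan requires adjustment for a variable available only after treatment, names a primary test that cannot carry it, and leaves the visit, cut-off and model open. None of this depends on an assumption about EAA and AHI.

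The size depends on how the rule is applied:
- constant OSA status in a within-girl model: no effect;
- uncentred OSA term with its intercept reported: the effect in 12-14 of 20 girls, with 65-72% power;
- each period's AHI: anything from no bias to a material loss. A 25% share, chosen for illustration, gives 2.1 points and about 52-67% power.

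Two stronger readings are tempting. One is that the primary estimate will be biased; that would need evidence that EAA alters AHI, and the documents offer none either way. The other is that the 86% is wrong; it is right for the unadjusted paired test, so this point does not call for a larger sample.

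**What to change.** Replace the adjustment sentence in the analysis plan with:

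> The primary and secondary treatment comparisons are the within-participant EAA-placebo contrasts, not adjusted for OSA or AHI. Analyses that include OSA status or AHI are sensitivity or exploratory effect-modifier analyses. Their visit, cut-off and model are named in advance and the covariate is mean-centred. They are interpreted knowing that no pre-treatment AHI is collected.

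The centring should apply to the covariate as entered in the regression of the paired difference, so that the intercept remains the average over all participants. Centring AHI itself in a repeated-measures model does not do this.

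Taking OSA status from the placebo period would not supply a baseline, because that visit follows EAA in girls randomised to EAA first. Whichever visit is named, this limitation should be stated.

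Reword section III.D, item 16, so that it describes OSA as a factor to be examined rather than one that must be adjusted for.

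The cost is one sentence in the analysis plan, a matching protocol edit and a little extra sensitivity analysis. No data collection changes, and the unadjusted contrast keeps the planned 86% power under the plan's own assumptions.
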